5 AMENDMENTS AND UPDATES

Any change to the protocol will be recorded in a written amendment, which will be signed by the Investigator/Health Care Provider and by the MAH/MAH REPRESENTATIVE. Amendment to the protocol may require regulatory submissions (e.g., Institutional Review Board [IRB]/ Independent Ethics Committee [IEC]) in accordance with local regulations. Submission package will include two documents: approved amended protocol and approved amendment (i.e., a summary of changes to the protocol).

In some cases, an amendment may require a change to the informed consent form (ICF).

6 MILESTONES

Milestone	Planned date
First Patient In (Start of data collection)	2015
Study Progress Report	In RMP update or applicable annual report
Last Patient In	2018
Last Patient Out (end of data collection)	2020
Database lock	2021
Final report of study results	2021

7 RATIONALE AND BACKGROUND

7.1 BACKGROUND

LEMTRADA is a recombinant humanized monoclonal antibody for intravenous infusion indicated for the treatment of patients with relapsing forms of multiple sclerosis (MS). LEMTRADA binds to CD52, a cell surface antigen present at high levels on T and B lymphocytes, and at lower levels on natural killer cells, monocytes, and macrophages. The mechanism by which LEMTRADA exerts its therapeutic effects in MS is unknown, but may involve immunomodulation through the depletion and repopulation of lymphocytes.

There are no adequate and well-controlled studies of LEMTRADA in pregnant women. It is not known whether LEMTRADA can affect reproductive capacity or cause fetal harm when administered to a pregnant woman. The effects of LEMTRADA on fertility and reproductive performance have been evaluated in the human CD52 (huCD52) transgenic mouse. In female mice, doses of 10 mg/kg/day of LEMTRADA administered for 5 days prior to cohabitation reduced gestational weight gain relative to the vehicle controls. Furthermore, Caesarean-sectioning and litter observations showed that the average number of corpora lutea and implantation sites per mouse were reduced following doses of 10 mg/kg/day for 5 days. Administration of 3 or 10 mg/kg LEMTRADA for 5 days in the huCD52 transgenic mouse during the period of fetal organogenesis (Gestation Day [GD] 6 through 10, or GD 11 through 15) resulted in no overt signs of maternal toxicity and, importantly, produced no gross external, soft tissue, or skeletal fetal effects. However, significant increases in the number of dams with all conceptuses dead or resorbed, along with a concomitant reduction in the number of dams with viable fetuses occurred in animals exposed to 10 mg/kg/day LEMTRADA during GD 11 through 15. The fetal loss was believed to be maternally mediated, as complete (or near complete) litter loss was only observed in a few dams, whereas an effect mediated by fetal response would likely result in numerous dams having lost a portion of their pups since the breeding strategy was such that not all pups expressed the huCD52 transgene. Exposure to LEMTRADA during presumed gestation and lactation resulted in alterations in total lymphocyte numbers and subpopulations during each of the periods of immune development evaluated. When dosed at 10 mg/kg/day for five days during lactation, LEMTRADA had no effect on the cognitive, physical, and sexual development of pups.

7.2 RATIONALE

Given the prevalence of MS in women of childbearing age, a greater overall number of exposed pregnancies can be expected following regulatory approval and market penetration. It is not known if LEMTRADA could harm an unborn child. Therefore, the lack of sufficient human fetal safety data for LEMTRADA makes pregnancy outcome monitoring an important component of research on the safety of LEMTRADA.

The proposed registry utilizes an international, observational cohort design to evaluate rates of adverse pregnancy outcomes in women exposed to LEMTRADA during pregnancy. These rates will be compared with corresponding rates in unexposed external comparison groups (details defined in Section 4, under "Data sources") to assess if the risk of any observed adverse pregnancy outcomes in women exposed to LEMTRADA exceeds rates observed in unexposed external comparison groups. Women exposed to LEMTRADA during pregnancy are eligible to enroll provided their pregnancy is ongoing. Women with early prenatal testing are permitted into the study; statistical analysis will be adapted to detect potential impact of prenatal testing on the pregnancy outcomes.

16-Nov-2016 Version number: 1

Pharmacokinetic data on LEMTRADA suggests that LEMTRADA plasma concentrations become undetectable at 1 month post-treatment but effective contraceptive use is the primary recommendation when receiving a course of treatment with LEMTRADA and for 4 months following that course of treatment (a period >5 half-lives). Therefore, exposure inclusion criteria for this study dictate that participants in this registry are eligible if they were or become pregnant at any time from initiation of a course of treatment with LEMTRADA through the 4 months period following their last LEMTRADA infusion for that course of treatment.

8 RESEARCH QUESTION AND OBJECTIVES

This PASS is an international, observational cohort study (registry) of pregnancy outcomes in women with MS exposed to LEMTRADA during pregnancy.

Pregnancy outcomes in women exposed to LEMTRADA will be compared with available data from external comparison groups: women with MS not exposed to LEMTRADA, and women without MS.

The overall goal of the registry is to compare maternal, fetal and infant outcomes in women exposed to LEMTRADA with the outcomes in women from unexposed external comparison groups during pregnancy and to assess if the risks of any adverse pregnancy outcomes and birth defects in women exposed to LEMTRADA during pregnancy exceeds the risks in women of unexposed external comparison groups. The registry will detect and record the following outcomes:

- Primary outcome:
 - Spontaneous abortion
- Secondary outcomes:
 - Major and minor congenital malformations;
 - Pregnancy outcome: stillbirth, elective terminations, preterm birth, full-term live birth;
 - Small for gestational age at birth;
 - Any other adverse pregnancy outcomes.

These outcomes will be assessed throughout pregnancy. Infant outcomes, including effects on postnatal growth and development, will be assessed through the first year of life.

9 RESEARCH METHODS

9.1 STUDY DESIGN

This post authorization safety study (PASS) is an international, observational cohort (registry) of pregnancy outcomes in women with MS exposed to LEMTRADA during pregnancy.

Pregnancy outcomes in women exposed to LEMTRADA will be compared with available data from external comparison groups: women with MS not exposed to LEMTRADA, and women without MS (details defined in Section 4, under "Data source").

This is an observational study with no experimental intervention utilized. Women enrolled in the study may receive treatment and evaluations for their MS and their pregnancies as determined by their treating physicians in accordance with local standard of care. Information of prospective pregnancies on patient's safety and pregnancy outcome will be collected during each trimester and within 6 weeks after the end of pregnancy. For all live births, the infant's HCP will be contacted at 1 year post delivery to obtain follow-up on the infant's health status. Information of retrospective pregnancies (exposed to LEMTRADA during pregnancy but pregnancy outcome is known at time of registry) will be collected similarly except for information on the chronological interview during pregnancy.

Women who were pregnant or became pregnant within the period of time between their initiating a course of treatment with LEMTRADA to 4 months after their last infusion for that course may be enrolled, provided their pregnancy is ongoing.

A total of approximately 204 women exposed to LEMTRADA during pregnancy (prospective) will be enrolled to achieve approximately 193 women followed up to 1 year post-delivery. Retrospective pregnancies are not part of this sample size calculation and are collected additionally.

Women exposed to LEMTRADA during pregnancy will be recruited from a variety of sources, including referral of female patients who become pregnant while enrolled in a separate observational study; referral of LEMTRADA-exposed female patients reporting pregnancies identified through routine pharmacovigilance activities, and LEMTRADA-exposed female patients reporting pregnancies identified through study outreach activities such as study postings on applicable websites. Enrollment as early in the pregnancy as possible is encouraged. Study enrollment is voluntary and requires informed consent in accordance with local requirements.

Information will be collected from applicable HCPs of the enrolled women. For enrolled women, data will be collected by National Coordinator via interview with women during each trimester and within 6 weeks after the completion of the pregnancy. Data on birth and neonatal outcomes will also be collected from the women's HCP within 6 weeks of pregnancy completion. For all live births, the infant's HCP will be contacted at 1 year post-delivery to obtain follow-up on the infant's health status.

Data will be collected on LEMTRADA exposure during pregnancy and subsequent pregnancy and fetal outcomes. Major structural malformations identified in the perinatal period through 12 months of life will be collected and classified. This study will also collect information on maternal history including demographic information, risk factors, and medications used.

9.2 SETTING

The registry will enroll pregnant women with MS who have had any pregnancy exposure to LEMTRADA from North America (NA), Europe (EU) and the rest of the world (ROW).

To maximize enrollment, this study employs an open enrollment approach. Any eligible woman, receiving health care in a country in which this study is operating, is encouraged to participate through her HCP(s) and the National Coordinator. The pregnant participant is followed until the end of pregnancy. If the outcome of pregnancy is a live born infant, the infant outcome, including effects on postnatal growth and development, will be assessed through the first year of life. Maternal enrollment and follow-up data may be reported by any of the woman's HCPs (e.g., obstetrician, neurologist, general/family physician, genetic counselor). Infant follow-up is provided by the infant's HCP whose expertise is typically in pediatrics or family medicine.

There is no forced selection process for patients or physician reporters in this protocol; therefore, prospectively enrolled women are expected to be representative of the source population in the respective countries.

9.2.1 Duration of the study

The total duration of the study is from the time the first woman exposed to LEMTRADA during pregnancy enrolls to when all enrolled women are followed up to 1 year post-delivery. The full study duration is expected to be approximately 5 years.

9.2.2 Eligibility criteria

9.2.2.1 Inclusion criteria

A woman is eligible for the study if all of the following apply:

- I 01. Women with MS who were or became pregnant within the period of time between the first infusion of a course of treatment with LEMTRADA to 4 months after their last infusion for that course.
- I 02. Able and willing to provide informed consent for study participation and the requirement of the study. Informed consent will be obtained at the time of enrollment in accordance with local regulatory requirements.

9.2.2.2 Exclusion criteria

E 01. Previous enrollment in this study for a previous pregnancy.

Property of the Sanofi Group - strictly confidential

9.2.3 Analysis population(s)

The primary analysis population will include all women (prospectively) enrolled in the study who meet the study inclusion criteria and have pregnancy outcome data recorded. Outcomes for the primary analysis population will primarily be compared with pregnancy outcomes in unexposed external comparison groups.

Ascertainment of pregnancy outcomes will be considered completed when:

- Pregnancy outcome is known and was not a live birth, or
- Pregnancy outcome was a live birth and the 1-year post-delivery follow-up has been completed, or
- The woman has been classified as lost to follow-up, or
- The woman has withdrawn informed consent prior to ascertainment of pregnancy outcome.

Otherwise; the pregnancy outcome will be considered as pending.

For the analysis, descriptive analyses of baseline characteristics of the additional populations of all enrolled women (including women whose pregnancy outcome data are unknown, such as lost to follow up), and the subset of women whose pregnancy outcome data are unknown, will also be calculated.

Retrospective pregnancy population will provide qualitative data which will be descriptively analyzed independent of the prospectively collected primary analysis population.

9.2.4 Modalities of recruitment

9.2.4.1 Investigator's selection

All awareness activities will be targeted to HCPs, including neurologists, in participating countries. MAH/MAH representative will attempt to raise awareness and encourage reporting by posting contact information: 1) on the study website; 2) in notices or publications in appropriate journals targeted to HCPs; 3) other websites as appropriate; 4) exhibits at clinical meetings. Other awareness avenues will be explored and utilized.

The study website previews to include general information regarding the study design, National Coordinators' contact information, enrollment eligibility and participation, instructions, patient informed consent forms, medical release forms.

To maximize enrollment, the registry employs an open enrollment approach. All enrollment and follow-up activities within a specific country are overseen by the country-specific National Coordinator. Multiple HCPs may be asked to report on an individual patient to the National Coordinator. It is anticipated that the reporters will be physicians or other HCPs with expertise in neurology, internal medicine, obstetrics, midwifery, pediatrics, family medicine, or genetic counseling.

Property of the Sanofi Group - strictly confidential

16-Nov-2016 Version number: 1

Patients in other observational studies identified as having exposure to LEMTRADA during pregnancy will be referred for potential enrollment into this registry for targeted follow-up and standardized analysis.

9.2.4.2 Patient selection

Women exposed to LEMTRADA during pregnancy will be recruited over a period of approximately 4 years from a variety of sources, including:

- Referral of female patients who become pregnant while enrolled in a separate international or local observational study Referral of LEMTRADA-exposed female patients reporting pregnancies identified through routine pharmacovigilance activities.
- LEMTRADA-exposed female patients reporting pregnancies identified through various outreach activities. For example, in some regions prescribing information and patient labelling may reference the pregnancy registry. Additional outreach strategies will include dissemination of information about the study and how to enrol through a variety of venues. Outreach materials for the study will direct HCPs and patients to the pregnancy cohort Study Coordinating Centre phone line and websites.

Study enrolment is voluntary and requires informed consent in accordance with local requirements. HCP, taking care of an eligible woman will explain the study protocol and eligibility criteria to women who contact or will be referred to them. A National Coordinator will be informed of a potentially eligible woman by such HCP. National Coordinator will instruct the HCP on obtaining informed consent and on collecting further data for this study. Women who meet the eligibility criteria and are interested in participating will be administered informed consent by HCP prior to conducting the first maternal interview. Informed consent including compliance with locally applicable data privacy legislation (e.g., in Europe, compliance with Directive 95/46/EC) will be obtained in accordance with local regulatory requirements. If applicable and where directed by local requirements, informed consent of fathers will also be obtained.

All eligible women who agree to participate and provide informed consent while the study enrolment period is open will be able to participate in the study. Information from women exposed to LEMTRADA during pregnancy who do not meet study eligibility criteria or decline participation will be handled as a separate pregnancy reports and referred to the MAH/MAH representative.

Variables: Rates of spontaneous abortion, major and minor congenital malformations, stillbirth, elective terminations, preterm birth, small for gestational age at birth, and any other adverse pregnancy outcomes for women exposed to LEMTRADA during pregnancy will be calculated. These rates will be compared with corresponding rates in unexposed external comparison groups (details defined in the Section 9.3).

9.3 DATA SOURCES

Exposed group:

For enrolled women (prospective pregnancies), data will be collected via interview during each trimester and at the pregnancy outcome interview which will occur within 6 weeks after the end of the pregnancy. Data on birth and neonatal outcomes will be collected from the women's/newborn's HCP during such pregnancy outcome interview. For all live births, the infant's HCP will be contacted at 1 year post-delivery to obtain follow-up on the infant's health status. Data will be collected on LEMTRADA exposure during pregnancy and subsequent pregnancy and fetal outcomes. All variables defined in this protocol (Section 8, primary and secondary outcomes) will be collected and classified. This study will also collect information on maternal history including demographic information, risk factors, and medications used. Information of retrospective pregnancies will be collected similarly except for information on the chronological interview during pregnancy, as pregnancy outcome is known at time of registry.

Comparison groups:

External comparison groups will be comprised (but not limited to) using the following sources:

- Data from the comparison groups enrolled in the AUBAGIO® (teriflunomide) North American registry "Teriflunomide Pregnancy Outcome Exposure Registry: an OTIS Autoimmune Disease in Pregnancy Project" (Genzyme study OBS13499):
 - Cohort II (North American AUBAGIO Pregnancy Outcome Exposure Registry Cohort II) - pregnant women with MS not exposed to AUBAGIO during the current pregnancy – modified to also exclude women exposed to LEMTRADA
 - Cohort III (North American AUBAGIO Pregnancy Outcome Exposure Registry Cohort III) pregnant women without MS and not exposed to AUBAGIO during the current pregnancy modified to also exclude women exposed to LEMTRADA

NOTE: Cohort I (pregnant women with MS exposed to AUBAGIO) are excluded

- Data from the population- based European Surveillance of Congenital Anomalies (EUROCAT) database (1).
- Data from the Metropolitan Atlanta Congenital Defects Program (MACDP) (2)

9.4 BIRTH DEFECT EVALUATION

If a birth defect is reported, the entire case is initially reviewed by the registry's Birth Defect Evaluator (BDE), an individual or individuals with expertise in teratology/dysmorphology. Following the BDE's review, the case is presented to the Scientific Advisory Committee (Section 3.4) for review and approval.

The BDE is charged with reviewing all details of the case and:

- Requesting further information as targeted follow-up, if needed;
- Coding each reported birth defect in accordance with the coding methodology used for Cohort II/III from the AUBAGIO registry;
- Identifying and documenting potential confounders, if available;
- Writing a brief narrative summarizing the review;
- Presenting the case to the Scientific Advisory Committee for further review and consensus.

For all reports of birth defects, the birth defect review process is conducted on birth defect status of each individual outcome. Therefore, a HCP may present a case as a birth defect, but after the BDE's review and coding, the registry may modify the final coding as "not a defect".

9.5 STUDY SIZE

9.5.1 Determination of sample size (LEMTRADA exposed)

The sample size of approximately 204 women exposed to LEMTRADA during pregnancy (prospective) is expected to achieve approximately 193 women followed up to 1 year post-delivery, allowing approximately 5% of recruited women to have missing pregnancy outcome data. With this sample size and a sample size of 117 in the comparator group, at 80% power and a 1-sided two-sample test with significance level of 0.025, we will be able to detect a 2.0-fold higher relative risk for a background spontaneous abortion rate of 13.5%, which encompasses the likely risk range for spontaneous abortions amongst women in the reference cohorts. In the reference cohorts of pregnancies from women with and without MS who were not exposed to LEMTRADA, where the rates of spontaneous abortion is expected to be 16.6% for women without MS (3) and 11.5% - 19.5% for women with MS (4,5,6). Retrospective pregnancies are not part of this sample size calculation and are collected additionally.

Table 1 shows the type of differences that may be detected comparing LEMTRADA-exposed pregnancies with various background rates for spontaneous abortion and any birth defects. For purposes of sample size calculation, a combination of general population background rates and rates published in the literature for women with MS with pregnancies unexposed to disease-modifying therapy were used.

16-Nov-2016 Version number: 1

Table 1 - Sample Size and Detectable Effect Size for Selected Endpoints

Endpoint	Population	Background Rate	Total Sample size	RR
Spontaneous abortion	General population	16.6% (3)	204 (Effective 193)	1.86
	Women with MS	11.5% (5)	204 (Effective 193)	2.12
	Women with MS	19.5% (4)	204 (Effective 193)	1.77
	Background Comparator Groups	13.5%	204 (Effective 193)	2.0
Any major birth defect General population		3% (8,9)	204 (effective 154)	4.05
	Women with MS	3% (10)	204 (effective 154)	4.05

RR: Relative Risk.

Sample size calculations were performed using EAST software version 6.2.

Assuming 5% drop out (outcome unavailable): 204*95%=193 patients will permit detection of RR=2.0 for a background rate of 13.5% with 80% power and 0.025 significance level based on 1-sided two sample Fisher's exact test (with comparator group sample size =117)

Assuming 80% live birth, 193*80%=154 live births.

References: In the MS treated women, the data from interferon B1A treated pregnant women showed discrepancy between the initial observation from a limited number of pregnancies from the clinical program and data collected in post-marketing setting. The rate of spontaneous abortions was 19.5% (8/41) from the clinical program (4), 11.5% (49/425) from prospective cases of PV databases (5), and 12.4% (28/226) from the pregnancy exposure registry (6).

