9.5.2 Sample size of external comparison groups (LEMTRADA non-exposed)

Sample size is set at 125 in comparison Cohorts II and III respectively in "AUBAGIO (teriflunomide) Pregnancy Outcome Exposure Registry: an OTIS Autoimmune Disease in Pregnancy Project" (Genzyme study OBS13499)." For the sample size calculation above, it is assumed that a sample size of 125 in the comparator group includes 4% missing data and 2% were exposed to LEMTRADA (in Cohort II), resulting in 125*96%*98% = 117 subjects.

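### Table 1's detectable relative risk of 4.05 for major birth defects puts the exposed group on a live-birth basis but apparently not the comparator; with both on that basis it is about 4.4 to 4.5 by Fisher's exact test

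*Protocol*

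**What the plan says.** Section 9.5.1 sets the operating characteristics "at 80% power and a 1-sided two-sample test with significance level of 0.025". The note under Table 1 names the test as a "1-sided two sample Fisher's exact test (with comparator group sample size =117").

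The exposed group is reduced in two steps. The first is for missing outcome: "Assuming 5% drop out (outcome unavailable): 204*95%=193 patients". The second applies to the birth-defect rows only: "Assuming 80% live birth, 193*80%=154 live births". Those two rows use a 3% background rate and read "204 (effective 154) 4.05".

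The comparator is derived in Section 9.5.2. The planned 125 "includes 4% missing data and 2% were exposed to LEMTRADA (in Cohort II), resulting in 125*96%*98% = 117 subjects". No live-birth fraction is applied to it there or in Table 1, and the birth-defect rows print no comparator size.

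Appendix A bases the primary analysis of defects on live births.

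Sections 4, 9.1 and 9.5.1 each give 193 as the number of women followed to 1 year. In Section 9.5.1 the sample of 204 "is expected to achieve approximately 193 women followed up to 1 year post-delivery". Section 9.3 provides the 1-year infant contact for live births only.

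**The concern.** A relative risk of defects among live births needs a live-birth denominator in both groups. Here one denominator is cut by 20% and the other seems to be left as a count of pregnancies. That amounts to assuming that every comparator pregnancy ends in a live birth, yet the headline calculation in the same section assumes 13.5% spontaneous abortion among comparators. Too large a comparator makes the detectable relative risk look smaller than it is.

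Major birth defects and spontaneous abortion are the only endpoints that Table 1 sizes. Readers will use 4.05 to judge what a finding of no difference can exclude, so the figure should be right even though it does not set enrolment.

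The label on the 193 is a related slip. It gives a count of women with a known pregnancy outcome the description of a 1-year follow-up count.

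**Working it through.** **Inputs.** 1-sided alpha 0.025, 80% power, Fisher's exact test, 204 × 95% stated as 193, and 193 × 80% = 154.4, stated as 154 (Section 9.5.1). Comparator 125 × 96% × 98% = 117.6, stated as 117 (Section 9.5.2). Background 3% and relative risk 4.05, so the exposed rate is 0.03 × 4.05 = 0.1215 and the difference is 0.0915 (Table 1).

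**Methods.** (a) Fisher: exact power by full enumeration of both binomials. (b) Pooled normal: power = Φ[(p1 − p0 − 1.96 × s0) / s1], with s0 = √{p̄(1 − p̄)(1/n1 + 1/n0)}, s1 = √{p1(1 − p1)/n1 + p0(1 − p0)/n0} and p̄ the pooled rate. Each is solved for the relative risk that gives 80% power.

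**Step 1: check the methods on the spontaneous abortion rows (193 v 117).**

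| Background | Table 1 | Fisher | Pooled normal |
|---|---|---|---|
| 16.6% | 1.86 | 1.87 | 1.84 |
| 11.5% | 2.12 | 2.16 | 2.10 |
| 19.5% | 1.77 | 1.78 | 1.75 |
| 13.5% | 2.0 | 2.02 | 1.98 |

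The stated values lie between the two methods, so 0.025 and 117 fit these rows.

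**Step 2: reproduce 4.05 with 154 v 117.** p̄ = 0.0820, s0 = 0.03365, s1 = 0.03069. Power = Φ[(0.0915 − 1.96 × 0.03365)/0.03069] = Φ(0.83) = 79.7%. The detectable relative risk is 4.06 by pooled normal and 4.14 by Fisher, where power at 4.05 is 78.1%. The stated figure is recovered with no live-birth reduction in the comparator.

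**Step 3: put the comparator on a live-birth basis.** The protocol gives no comparator live-birth fraction, so two assumptions bracket it:
- the exposed group's 80%: 117 × 0.80 = 93.6, about 94
- removal of the 13.5% spontaneous abortions only: 117 × 0.865 = 101.2, about 101

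Pooled normal power at 4.05:
- 154 v 94: s0 = 0.03685, s1 = 0.03167; Φ[(0.0915 − 0.0722)/0.03167] = Φ(0.61) = 72.9%
- 154 v 101: s0 = 0.03576, s1 = 0.03132; Φ[(0.0915 − 0.0701)/0.03132] = Φ(0.68) = 75.3%

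| Exposed v comparator | Detectable RR, Fisher | Detectable RR, pooled normal | Power at 4.05, Fisher | Power at 4.05, pooled normal |
|---|---|---|---|---|
| 154 v 117 | 4.14 | 4.06 | 78.1% | 79.7% |
| 154 v 101 | 4.41 | 4.28 | 71.6% | 75.3% |
| 154 v 94 | 4.48 | 4.40 | 70.3% | 72.9% |

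Within one method, the comparator correction moves the detectable relative risk from 4.14 to 4.41–4.48 (Fisher) or from 4.06 to 4.28–4.40 (pooled normal). With 94 comparators the shift is 0.34 by either method, about 8%.

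**Step 4: check other routes to 4.05.** A one-sample exact test of 154 against a fixed 3% gives 2.68, so these rows are not a comparison with a fixed population rate. Fisher with 154 v 94 at 1-sided 0.05 gives 4.05, but the protocol states 0.025.

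**Step 5: the 193.** It equals 204 less 5% with no pregnancy outcome. Of these, 154 are assumed to have a live birth, so 193 − 154 = 39 have no live-born infant to follow to 1 year.

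**The case against.** - **The comparator size is inferred.** The birth-defect rows print none, and a different alpha with 94 comparators also gives 4.05. This stands as a caution. But 117 is the only comparator size in the protocol, and it reproduces 4.05 at the stated alpha.
- **The 80% is written for exposed women only.** Correct. A reader might infer that 4.5 is the one right value; the document does not support that, and a range is the honest answer. Keeping 117 would still need no comparator pregnancy losses at all, which contradicts the 13.5%.
- **Setting 4.05 against 4.5 mixes methods.** Also correct: 4.05 matches the pooled normal result and 4.48 is Fisher. The like-for-like shift is smaller.
- **Other comparison sources exist.** Section 9.3 also names EUROCAT and MACDP, which are not limited to 117 women. That tempers the consequence, but step 4 shows that the 4.05 rows do not represent such a comparison.
- **The 193 can be read loosely.** Section 9.2.3 treats ascertainment as complete once an outcome other than live birth is known. A reader might infer that the protocol promises something impossible, or ignores loss during the infant year. Neither follows: 193 can mean follow-up completed as applicable, and Section 9.9 discusses that loss and plans an analysis of infants with complete 1-year follow-up. What remains is a misleading label.
- **Harsher scenarios.** One could add losses in the infant year, or carry the spontaneous abortion alternative into the live-birth count. The first needs a loss rate that the protocol does not give, and the second joins endpoints that Table 1 treats separately. Neither is an error in the document.

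**Conclusion.** The point holds as a correction of stated figures. With both groups on a live-birth basis, the detectable relative risk at a 3% background is about 4.4 to 4.5 by Fisher, the test that the protocol names, or 4.3 to 4.4 by pooled normal. At 4.05 the chance of missing the effect is about 28 to 30% by Fisher, or 25 to 27% by pooled normal, against the intended 20%.

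This rests on 117 having been used in the birth-defect rows and on a comparator live-birth count between 94 and 101. The description of the 193 is inconsistent with the 154 live births in the same section and should be reconciled.

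A reader might infer that the study is undersized or that this must be fixed before it can proceed. The document does not support that. Birth defects are a secondary outcome, enrolment is set by the spontaneous abortion calculation, which is untouched, and the planned relative risks and confidence intervals in Section 9.7.5 do not change. The broad message also survives: only an increase of roughly four-fold or more is detectable. Severity is minor to moderate.

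**What to change.** 1. In Table 1, recompute the two birth-defect rows with live births in both groups. Print the comparator live-birth number, the live-birth fraction assumed for it and the test used. With 94 to 101 comparator live births, the entry becomes about 4.4 to 4.5 by Fisher.
2. In Sections 4, 9.1 and 9.5.1, describe the 193 as women with a known pregnancy outcome, of whom about 154 are expected to have a live birth eligible for 1-year infant follow-up.

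The cost is a recalculation and a few edited sentences, with a slightly less favourable figure in two rows. No additional patients or data are needed, and the primary calculation stays as it is.
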